Therapy with (Li-ESWT) for erectile dysfunction has been proposed as a new alternative in the management of erectile dysfunction (12, 22-25). Its mechanisms of action can be multiple, but are summarized in the increase in vascular flow to the corpora cavernosa generated by a process of neovascularization (26) secondary to angiogenesis promoted by endothelial growth factors such as vascular endothelial growth factor (VEGF), endothelial cell growth factors and cell proliferation nuclear antigen (27), in addition to the increase in the concentration of vasodilator substances such as nitric oxide. The therapy with Li-ESWT has been presented as a therapeutic option, which does not replace the other alternatives, but which adds efficacy to traditional ED management (28).

Likewise, therapy with radial waves arises as a new option for the management of this disease, which has been conducted by different specialists given the benefit shown in the increase of blood flow and muscle recovery for different musculoskeletal conditions. However, currently there are no controlled studies that report on the efficacy and safety of this therapy for the treatment of erectile dysfunction (16, 17). For this reason, it is pertinent to carry out a clinical trial that allows obtaining valid results and thus making reliable clinical decisions.

Objectives

Primary

To evaluate the effectiveness of radial shock wave therapy in patients with moderate erectile dysfunction ² measured as the increase in the average IIFE-EF score at the end of the treatment.

Secondary

- 1. To evaluate the effectiveness of radial shock wave therapy at one month of follow-up, with respect to the change in the average IIFE-EF score.
- 2. To evaluate the efficacy of radial shock wave therapy with respect to the average score of the erection hardness scale (EHS), at the end of the treatment and at one month of follow-up, in the intervention and control groups.
- 3. To evaluate the effectiveness of radial shockwave therapy, regarding the change in the use of sildenafil at the end of treatment and at one month of follow-up, in the intervention and control groups.
- 4. To compare the incidence of adverse events in the intervention and control groups.

² For this study moderate erectile dysfunction is considered a score on the IIEF-EF scale from 11 to 21, which includes the mild to moderate and moderate categories.

Materials and methods

Type of study

Randomized, double-blind clinical trial.

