It will be determined by the presence of adverse events. These will be evaluated at the end of each of the therapies and a month of follow-up. This variable will be dichotomous as the presence or absence of adverse events. Additionally the type of adverse event and the degree of severity will be recorded.

Randomization

The assignment of patients to the treatment arms will be done with the method of randomization by balanced blocks of unequal cells. The assignment of the treatment will be centralized, so once the patient agrees to participate in the study and signs the informed consent, an email should be sent to the research center ([contact]) who will only inform the therapist which is the group (intervention or control) that corresponds to the patient.

To conceal the assignment sealed opaque envelopes will be used, this envelope will be opened once the request is generated in each center, after the patient has voluntarily accepted to participate in the study and the informed consent process has been carried out with signature of the written document.

Neither the patient, the attending physician, nor the professional who applies the questionnaires will know the group to which the patient was assigned.

Techniques, procedures, data collection and processing

The subjects who attend consultation for erectile dysfunction at the Boston Medical Group clinics in Bogotá (Colombia) and Lima (Peru), will be treated as usual according to the institutional management protocols and screened to determine if they meet the eligibility criteria. If so, they will be invited to participate in the research project and the informed consent process will be carried out in which the objectives, risks, benefits, procedures and other relevant research data will be explained.

Once the patient has voluntarily accepted to participate in the study and the informed consent document has been signed, an email will be generated to the research center to request the group to which the patient will be assigned.

A baseline measurement of the IIEF-EF and the EHS will be made before starting the intervention; In addition, the AMS questionnaire should be completed to rule out hypogonadism. Once the treatment is completed, patients must complete the IIEF-EF and EHS scales in the last treatment session. In this same session, the patient will be evaluated for adverse events; later, they will have

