The research subjects will be followed up one month after the end of the treatment. In the event that the patient cannot attend the follow-up, the respective scales will be sent to his e-mail so he can process them and return them by the same means; if after 3 days no response is received, a research assistant will call him and apply the questionnaires by telephone.

Statistical Analysis

A descriptive analysis of the individuals' baseline characteristics linked to each treatment arm will be made, estimating measures of central tendency and dispersion in the case of continuous variables, and measures of relative and absolute frequency for categorical variables.

To evaluate the effectiveness of the therapy, the change in the IIEF-EF scale will be compared at the end of the treatment with the baseline score for each of the arms, using parametric tests in case the

data present a normal distribution, or nonparametric tests otherwise. This same analysis will be done for the scores at the one-month follow-up.

For the EHS scale, the change in at least 1 point will be evaluated, in any of the established measurements. The association between the change in the score and the received treatment will be evaluated estimating the relative risk with its respective confidence interval.

The percentage of patients that decrease or discontinue the use of sildenafil in each group will be estimated, comparing the proportion between the groups at the end of the therapy scheme and the month of follow-up, using the Chi-square test.

The incidence of adverse events for each of the intervention groups will be estimated and the value between them will be compared using the Chi-square test.

In addition to the comparison between groups, stratified analyzes will be performed with multivariate regression models to determine how each intervention adjusted for covariates, such as comorbidities or additional treatments.

An interim analysis will be done once 60% of the total number of patients has completed the treatment (main outcome).

Expected impact

The main contribution of this study is for the scientific community and for patients with erectile dysfunction, by collecting scientific evidence of quality that allows to make a decision about the use of radial waves for the management of erectile dysfunction.

Ethical aspects

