The research will be conducted in compliance with the legal and ethical guidelines described in Resolution 8430 of 1993 of the Colombian Ministry of Health and other national regulations; The principles for human research enunciated in the Declaration of Helsinki of the World Medical Association, and the ethical guidelines contemplated by the Council of International Organizations of Medical Sciences -CIOMS and the Belmont Report- will be respected and complied with.

According to Article 11 of Resolution 8430 of 1993 of the Ministry of Health, it is considered that this is an investigation with risk greater than the minimum for the research subjects, which fully respects the provisions of article 8 of the same. On the other hand, and in accordance with this legislation, approval will be requested from an Ethics Committee that authorizes the development of the investigation.

The intervention to be evaluated has a proven effectiveness in other conditions and the reports published in scientific evidence show that the rate of adverse events is very low. The intervention will be administered by personnel with all the technical capacity and experience required, both for the administration of the intervention and for the management of possible adverse events.

Each subject will be informed of all possible consequences (regardless of their probability of occurrence) of participating in this investigation. An informed consent will be explained and completed and the individual will be free to accept participation in the study without causing any inconvenience with their treatment (Annex 5).

Likewise, the confidential management of the information collected in response to the need not to violate the privacy of each research subject will be guaranteed. The databases will be kept in the Boston Medical Group offices and will only be accessed by the researchers participating in the study.

It is guaranteed that the researchers possess the technical competence required for this study and that they have the necessary tools for the care and use of research data.

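### The between-arm safety comparison is a chi-square test with no effect estimate or confidence interval, so the planned analysis cannot show what excess adverse event risk is excluded

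*Combined protocol and SAP*

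**What the plan says.** Safety is in the title and in the overall objective. Among the secondary objectives, the fourth is "To compare the incidence of adverse events in the intervention and control groups". No safety margin is given.

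The Safety section defines the variable per patient: "This variable will be dichotomous as the presence or absence of adverse events". It adds: "Additionally the type of adverse event and the degree of severity will be recorded".

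The Statistical Analysis section gives the method in one sentence. Incidence is to be estimated by arm; for the comparison, "the value between them will be compared using the Chi-square test". It names no between-arm effect measure, interval or rule for few or no events, and does not say whether a continuity correction applies. In the same section the plan for a change in EHS is different: the association with treatment is assessed by "estimating the relative risk with its respective confidence interval".

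On the expected rate, Ethical aspects says that "the reports published in scientific evidence show that the rate of adverse events is very low". No figure is attached.

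The Sample size section is built on the IIEF-EF change alone: 33 per group, raised to 40 per group for losses, 80 in total.

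**The concern.** The plan will produce two incidences and a p-value. A p-value above 0.05 does not tell the reader how large an excess of adverse events on radial waves remains compatible with the data. In a trial sized only for efficacy, that is the main thing a reader needs from the safety comparison. The section on expected impact says the results are meant to inform a decision on using the therapy, and the plan offers no other between-arm summary of safety to inform it.

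A second, conditional issue is that chi-square is a large-sample test. If adverse events are as rare as Ethical aspects suggests, the expected counts are small, and with no events in either arm the statistic does not exist.

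**Working it through.** **Inputs.** From the plan: 40 per arm enrolled; 33 per arm as the size before the allowance for losses; a yes/no variable per patient; chi-square test. Assumed, because the plan is silent: two-sided 5% level, Pearson's form without continuity correction, and the true event rates shown. The plan states no safety figure to reproduce.

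**1. Power.** Sum the binomial probabilities of every pair of event counts (a, b), each from 0 to 40, for which p < 0.05.

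| True risk, radial v placebo | Chi-square power, 40 per arm | Fisher power, 40 per arm |
|---|---|---|
| 5% v 1% | 10% | 0.9% |
| 10% v 2% | 34% | 11% |
| 10% v 5% | 15% | 4% |
| 30% v 20% | 18% | 12% |

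With 33 per arm, chi-square power is 26% for 10% v 2% and 16% for 30% v 20%. Low power therefore does not depend on events being rare.

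**2. What an interval would show.** Take 3 events v 1 event among 40 per arm.

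- Risks are 3/40 = 7.5% and 1/40 = 2.5%; the difference is 5.0 points.
- Pooled risk is 4/80 = 5%. Chi-square = 0.05² / (0.05 × 0.95 × 2/40) = 0.0025 / 0.002375 = 1.05, so p = 0.30.
- Wilson 95% limits are 2.6% to 19.9% for 3/40 and 0.4% to 12.9% for 1/40.
- Newcombe lower limit: 5.0 - √[(7.5 - 2.6)² + (12.9 - 2.5)²] = -6.5 points.
- Newcombe upper limit: 5.0 + √[(19.9 - 7.5)² + (2.5 - 0.4)²] = +17.5 points.

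Other tables, same method:

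| Events, radial v placebo | Chi-square p | Risk difference, 95% Newcombe (points) |
|---|---|---|
| 0 v 0 | undefined | 0 (-8.8 to +8.8) |
| 3 v 1 | 0.30 | 5.0 (-6.5 to +17.5) |
| 9 v 6 | 0.39 | 7.5 (-9.9 to +24.5) |

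**3. Small expected counts.** With equal arms, the expected events per arm are 40 × the pooled rate. This is below 5 when the pooled rate is below 5/40 = 12.5%.

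**4. Undefined statistic.** This requires no events among all 80 patients, with probability (1 - p)^80 at a common rate p: 0.99^80 = 45%, 0.98^80 = 20%, 0.95^80 = 1.7%.

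**5. Type I error.** The same enumeration with equal rates in both arms gives an actual size for the nominal 5% chi-square of 0.09% at a 1% rate, 0.74% at 2%, 4.3% at 5% and 5.9% at 10%. The maximum over rates from 1% to 12% is about 5.9%.

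**The case against.** The strongest reply has four parts.

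- **The p-value is not the only output.** This is right. Incidence per arm is planned, and type and severity are recorded. With 0 v 0 events the report would still show 0/40 and 0/40. What is missing is an estimate of the difference with its uncertainty. The regression models mentioned in the same section do not fill the gap: they are not tied to adverse events.

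- **The low rate is not established for this endpoint.** This also stands. The statement that reports "show that the rate of adverse events is very low" has no figure and concerns published experience with the intervention. The trial counts any adverse event in patients who all take sildenafil. If the pooled rate exceeds 12.5%, the expected-count issue falls away. The precision issue does not, as the 30% v 20% and 9 v 6 rows show.

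- **Chi-square is not invalid here, and Fisher's test would be worse at finding an excess.** A reader might infer from small expected counts that the planned test is unreliable and must be replaced by an exact one. The plan's figures do not support that. True size stays at or below about 5.9% at the rates examined and is mostly conservative. Fisher's test cuts power from 34% to 11% for 10% v 2%.

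- **Nobody has said that non-significance means safe.** Correct: a reader might infer such an intention, but the documents contain no such statement and no non-inferiority claim. Low power for adverse events is also usual in a trial sized on efficacy. Neither fact explains why safety gets no interval when EHS does.

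**Conclusion.** The point holds as a gap in the planned safety analysis. There is no between-arm effect estimate or confidence interval for adverse events, and nothing elsewhere in the document supplies one. At the planned size, chi-square power is about 10% to 34% in the scenarios above, and non-significant tables remain compatible with excesses of roughly 18 to 24 percentage points. Even no events at all leaves ±8.8 points.

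The sparse-data problem is conditional. Expected counts below 5 need a pooled rate under 12.5%. An undefined statistic needs zero events in both arms, which is plausible at rates of 1% to 2% and unlikely at 5%.

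The figures assume 40 patients analysed per arm, a two-sided 5% level and the listed event rates, none of which the plan gives for safety. With 33 per arm the picture is somewhat worse: the 0 v 0 interval widens to ±10.4 points. This is a worthwhile, inexpensive correction and does not call the trial's validity into question.

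**What to change.** In Statistical Analysis, replace the adverse event sentence with text to this effect: the proportion of patients with at least one adverse event will be reported by arm; the main safety comparison will be the risk difference (radial waves minus placebo) with a 95% confidence interval valid for small counts, such as Newcombe's; the safety conclusion will rest on that interval, in particular its upper limit, and a non-significant p-value will not be taken as evidence of equal safety.

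Any p-value is supplementary. If chi-square is kept, state whether a continuity correction applies and that no test will be reported when neither arm has an event. A change to Fisher's test is not required.

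The cost is SAP wording and slightly more analysis, with no new data and no change in sample size or conduct. The intervals will be wide, so the safety statement will be less favourable than a bare non-significant p-value might suggest. The fix does not add power; it makes the remaining uncertainty visible.
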